### **11.3 DEATHS AND SERIOUS ADVERSE EVENTS**

A summary of deaths will include the number of subjects who died, the primary reason for death, the number of deaths within 30 days of the last dose of study treatment, the number of subjects alive at last contact with follow-up ongoing, the number of subjects alive at last contact with follow-up ended. The frequency and percentage of serious TEAEs (all grades) will be summarized in descending order of total incidence by PT. A similar analysis will be repeated for treatment-related serious TEAE by PT, for serious TEAE related to IMO-2125 by PT, and for serious TEAE related to Ipilimumab by PT. Grade 3 or above serious TEAEs will also be summarized. Summaries of deaths and SAEs will be repeated for subjects who received visceral injection during the study drug administration. Deaths will also be listed. The listing of SAEs will include a flag for those that are treatment-emergent and will display the SAE's relationship to study treatment.

The following summaries will be provided:

- Serious Treatment-Emergent Adverse Events by Preferred Term
- Grade 3 or Above Serious Treatment-Emergent Adverse Events by Preferred Term
- Treatment-Related Serious Treatment-Emergent Adverse Events by Preferred Term (including Treatment-Related, IMO-2125-Related, and Ipilimumab-Related)
- Treatment-Related Serious Treatment-Emergent Adverse Events by Preferred Term and Maximum Grade
- Deaths

The following listings will be provided:

- All SAEs
- TEAEs Leading to Death
- All Deaths

### **11.4 ADVERSE EVENTS LEADING TO DISCONTINUATION OF STUDY TREATMENT (WITHDRAWAL), DOSE INTERRUPTIONS, OR DOSE REDUCTIONS**

Dose reductions are only permitted for subjects enrolled under Protocol Version 2.0. TEAEs leading to dose interruption and dose reduction will be listed. The following category of TEAEs will be summarized by PT:

- TEAEs Leading to Permanent Discontinuation of IMO-2125 by Preferred Term

Idera Pharmaceuticals, Inc.  
Statistical Analysis Plan  
Protocol Number: 2125-MEL-301

- 
- IMO-2125-Related TEAEs Leading to Permanent Discontinuation of IMO-2125 by Preferred Term
  - TEAEs Leading to Permanent Discontinuation of Ipilimumab by Preferred Term
  - Ipilimumab-Related TEAEs Leading to Permanent Discontinuation of Ipilimumab by Preferred Term

The following listings will be provided:

- TEAEs Leading to Dose Interruption or Dose Reduction
- TEAEs Leading to Treatment Discontinuation

### **11.5 IMMUNE-RELATED ADVERSE EVENTS**

Immune-related AEs (irAEs) are side effects associated with the increased activity of the immune system by immunotherapy agents such as checkpoint inhibitors, which can affect multiple organs of the body including the skin, gastrointestinal tract, endocrine system, liver, lungs, nervous system, and musculoskeletal system.

The following list of AEs were provided in the protocol as a guide to the investigators to identify the immune-related AEs. Any AEs which have been associated with the use of immunotherapy agents were marked as immune-related in the CRF.

- Adrenal insufficiency
- Hypophysitis
- Hypopituitarism
- Hypothyroidism
- Hyperthyroidism
- Other endocrinopathies
- Colitis
- Enterocolitis
- Dermatitis
- Autoimmune dermatitis
- Guillain Barre syndrome
- Hepatitis
- Myasthenia gravis
- Pneumonitis
- Stevens Johnson Syndrome
- Toxic epidermal necrolysis
- Uveitis
- Iritis
- Myocarditis
- Any AEs that the Investigator considers to be of autoimmune or immune-related origin

Idera Pharmaceuticals, Inc.  
 Statistical Analysis Plan  
 Protocol Number: 2125-MEL-301

In addition, the Sponsor medical team also reviews all the events coded under 17 selected MedDRA SOCs that have the potential to identify irAEs (see the list of SOCs below). These AEs are reviewed relative to the dosing of either ipilimumab or tilsotolimod. They are also assessed in the context of the usage of concomitant medications and other AEs that occurred around the same time. This process allows for a holistic review of events in the context of other data elements, thereby providing an exhaustive process for potential irAE identification.

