10.1.3.4. Immune-related AEs

Immune-related AEs (irAEs) are side effects associated with the increased activity of the immune system by immunotherapy agents such as checkpoint inhibitors, which can affect multiple organs of the body including the skin, gastrointestinal tract, endocrine system, liver, lungs, nervous system, and musculoskeletal system. The following list of AEs, which have been associated with the use of immunotherapy agents, will be considered to be immune-related and should be considered as such unless another etiology can be clearly established:

- Adrenal insufficiency
- Hypophysitis
- Hypopituitarism
- Hypothyroidism
- Hyperthyroidism
- Other endocrinopathies
- Colitis
- Enterocolitis
- Dermatitis
- Autoimmune dermatitis
- GuillainBarre syndrome
- Hepatitis
- Myasthenia gravis
- Pneumonitis
- StevensJohnson Syndrome
- Toxic epidermal necrolysis
- Uveitis
- Iritis
- Myocarditis
- Any AEs that the Sponsor or investigator considers to be of autoimmune or immune-related origin.

Immune-related AEs will be identified as such in the eCRF, and the associated treatment for these AEs should be recorded including the drugs, doses, duration, and AE(s) being treated. Any dose modifications to either study treatment should also be recorded including the start and end dates of the modification, the study drug doses, and any dose reductions. See Section 9.3.4 for additional information about dose modifications.

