**Table 2 List of MedDRA SOCs Used by Sponsor in Identification of Additional Potential irAEs**

MedDRA SOCs
Cardiac disorders
Endocrine disorders
Eye disorders
Gastrointestinal disorders
General disorders and administration site conditions
Hepatobiliary disorders
Immune system disorders
Injury, poisoning and procedural complications
Investigations
Musculoskeletal and connective tissue disorders
Neoplasms benign, malignant and unspecified (incl cysts and polyps)
Product issues
Renal and urinary disorders
Respiratory, thoracic and mediastinal disorders
Skin and subcutaneous tissue disorders
Surgical and medical procedures
Vascular disorders

The number and percentage of subjects who experienced at least one irAE will be tabulated. The preferred terms will be identified using the search strategy as described above. The frequency and percentage of immune-related TEAEs will be summarized by PT, as well as by PT and maximum grade. Similar analyses will be repeated for Grade 3 or above immune-related TEAEs and for Grade 3 or above treatment-related immune-related TEAEs. The frequency and percentage of treatment-related immune-related TEAEs will be summarized by PT and maximum grade.

Similarly, the frequency and percentage of immune-related serious TEAEs will be summarized by PT and maximum grade. Similar analysis will be repeated for Grade 3 or above immune-related serious TEAEs by PT. The number and percentage subjects who experienced immune-related TEAEs leading to permanent discontinuation of IMO-2125 and

Idera Pharmaceuticals, Inc.  
 Statistical Analysis Plan  
 Protocol Number: 2125-MEL-301

---

subjects who experienced immune-related TEAEs leading to permanent discontinuation of ipilimumab will be presented by PT.

A listing of immune-modulating medications which include thyroid hormone replacement therapies, systemic steroid and immuno-suppressants used after occurrence of irAE will be presented. Thyroid hormone replacement therapies will be identified by WHO drug ATC prefix H03, systemic steroids by WHO drug ATC prefix H02, and immuno-suppressants by WHO drug ATC prefix L04.

All irAEs will be listed. This listing will include treatment arm, age, sex, verbatim term and the corresponding coded terms, start date and study day, end date and study day, grade, serious (yes or no), relationship to treatment (yes or no), action taken, and outcome. It will also include an indicator for the source of the irAEs (CRF or sponsor-defined).

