Hypoxia	An Oxygen saturation (SaO 2 ) <94% or an individual requiring supplemental oxygen to correct a deficit in oxygenation is considered to have hypoxia. Oxygen provided only as a comfort measure should not be used.
Anaphylactic reaction	Anaphylaxis is a serious, acute allergic reaction without a particular immunologic mechanism and based on the following clinical features: 
 
1. Acute onset of an illness (minutes to several hours) with involvement of the skin, mucosal tissue, or both, and at least one of the following:               
 
• Hypoxia
 
• Hypotension
 
 
 
2. Two or more of the following that occur rapidly after exposure to Tilsotolimod (minutes to several hours):               
 
• Involvement of the skin-mucosal tissue
 
 
 

Idera Pharmaceuticals, Inc.  
 Statistical Analysis Plan  
 Protocol Number: 2125-MEL-301

AE Term	Definition
	
 
• Hypoxia
 
• Hypotension
 
• Persistent gastrointestinal symptoms
 

	
 
3. Hypotension after exposure to Tilsotolimod when prior systemic reactions with Tilsotolimod has occurred (minutes to several hours)
 

In order to perform a more comprehensive assessment of the AESIs, a search of all TEAEs which are coded under any of the following MedDRA SOC and started within 14 days after any tilsotolimod injections will also be conducted:

- General disorders and administration site condition
- Respiratory and mediastinal disorders vascular disorders
- Immune system disorders (see [Table 2](#) in Section 11.5)

The AEs identified will be reviewed and classified by the Sponsor as CRS, anaphylactic reaction or hypersensitivity reaction. The classification will be imported into the analysis dataset for summaries.

Significant AESIs will be summarized, that include Grade 3 and above systemic injection and infusion reactions.

Based on the strategy and definitions stated above, these AEs included under each event type will be determined based on a programmatic search of the AE datasets using the specified LLT in conjunction of a medical review of the AEs identified. The incidence of the AESIs under each event type will be summarized by MedDRA preferred term.

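### The sponsor's 17-SOC screen for immune-related AEs (SAP 11.5, Table 2) omits Nervous system disorders, so an unmarked neurological event may be missing from the irAE tables

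*SAP*

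**What the plan says.** Protocol 10.1.3.4 describes irAEs as effects of immunotherapy "which can affect multiple organs of the body including the skin, gastrointestinal tract, endocrine system, liver, lungs, nervous system, and musculoskeletal system". It lists terms that "will be considered to be immune-related and should be considered as such unless another etiology can be clearly established", and ends with a catch-all under which the sponsor or the investigator may classify any AE as immune-related. SAP 11.5 repeats the organ description and the list, though its catch-all names the investigator only.

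SAP 11.5 then gives two routes into the irAE set.

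- **CRF mark.** "Any AEs which have been associated with the use of immunotherapy agents were marked as immune-related in the CRF".
- **Sponsor screen.** In addition, "the Sponsor medical team also reviews all the events coded under 17 selected MedDRA SOCs that have the potential to identify irAEs". The classes are in Table 2, titled "List of MedDRA SOCs Used by Sponsor in Identification of Additional Potential irAEs". The events are read against dosing, concomitant medications and other AEs at about the same time, "thereby providing an exhaustive process for potential irAE identification".

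On the tables, SAP 11.5 says: "The preferred terms will be identified using the search strategy as described above". SAP 11.2 also points to Table 2 of Section 11.5 for the immune-related rows of the overview table. The irAE listing will show each event's source, either CRF or sponsor-defined.

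**The concern.** Nervous system disorders is not among the SOCs in Table 2, although the definition in the same section names the nervous system. The list is otherwise broad: it includes Product issues, Surgical and medical procedures, and Neoplasms. No reason for the omission is given.

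The trial adds an immune stimulant to ipilimumab, so irAE incidence by arm is a central safety output. If a site does not mark a neurological event coded to the missing SOC, no step in the SAP requires anyone to consider it as an irAE. The event would still be reported as an AE, but it could be absent from the irAE counts that the IDMC and readers of the study report will use.

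**Working it through.** **1. The plan's own count.** The text of SAP 11.5 says 17 SOCs and Table 2 has 17 entries. The two agree, so no row was lost when the PDF was read.

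**2. Organ systems against SOCs.** The seven systems named in protocol 10.1.3.4 and SAP 11.5, set against Table 2:

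| Organ system named | SOC in Table 2 |
|---|---|
| Skin | Skin and subcutaneous tissue disorders |
| Gastrointestinal tract | Gastrointestinal disorders |
| Endocrine system | Endocrine disorders |
| Liver | Hepatobiliary disorders |
| Lungs | Respiratory, thoracic and mediastinal disorders |
| Nervous system | none |
| Musculoskeletal system | Musculoskeletal and connective tissue disorders |

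Six of seven match. Adding the missing class gives 17 + 1 = 18 SOCs and seven of seven.

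**3. Does another step cover the gap?**

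- *Investigator list.* It has 19 named terms and one catch-all. Two of the 19 are neurological: Guillain-Barre syndrome and myasthenia gravis. Neuropathy is not named there, although protocol Table 4 places neuropathies with other immune-related toxicities for ipilimumab dose modification.
- *CRF mark.* The screen exists to find additional irAEs, so the SAP does not treat the mark as complete.
- *AESI search, SAP 11.6.* This is "a search of all TEAEs which are coded under any of the following MedDRA SOC and started within 14 days after any tilsotolimod injections". It is aimed at cytokine release and anaphylactic reactions, its SOC list has no nervous-system class, and its 14-day window after an injection cannot apply to the ipilimumab-alone arm.
- *Protocol catch-all.* The sponsor may label any AE, but SAP 11.5 describes no sponsor route other than the 17-SOC review.

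**4. Outputs that depend on the screen.** SAP 16.2 plans nine dedicated irAE tables: 14.3.2.6.1, 14.3.2.6.2, 14.3.2.6.3, 14.3.2.7.1, 14.3.2.7.2, 14.3.5.4, 14.3.5.5, 14.3.6.5 and 14.3.6.6. The first five are marked for the IDMC. Overview table 14.3.2.1, also for the IDMC and marked topline, carries irAE rows. Table 14.1.8.2 (medications for irAEs) is not counted, because SAP 9.5 builds it from the Concomitant Medication eCRF page.

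**5. Scale of one missed event.** The documents give no rate of neurological irAEs and no rate of unmarked events, so the under-count cannot be computed. The effect of one subject whose only irAE is missed is:

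- planned per arm: 454 / 2 = 227, and 1 / 227 = 0.44 percentage points;
- with an assumed Safety Set of 90% of plan: 0.90 × 227 = 204, and 1 / 204 = 0.49 percentage points.

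**The case against.** The strongest reply is that little is left to be missed. The listed neurological terms are immune-related by default under protocol 10.1.3.4. Table 4 alerts investigators to neuropathies and, as far as the broken table can be read, requires permanent ipilimumab discontinuation for the more severe or persistent ones, which then appear in the discontinuation tables. SAEs reach the pharmacovigilance vendor whatever their SOC. The IDMC receives all TEAEs by SOC and preferred term (14.3.2.2.1), and the AE listing shows irAE status, so an unmarked event remains visible. What remains is mainly a non-serious, unmarked event that does not lead to discontinuation, and its only loss is a descriptive label. All of this stands, and it limits the size of the problem.

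The screen is also an extra layer that the protocol does not require, and *exhaustive* could be read as describing the depth of review rather than the breadth of the SOC list. The first part is true. The second is a possible reading, but the section also uses the screen to define what enters the irAE tables, so breadth matters.

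Finally, the documents do not show which terms MedDRA codes to which SOC. That is correct, so the claim is confined to events that are coded to the missing SOC. None of these safeguards requires an unmarked neurological event to be considered for the irAE label.

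**Conclusion.** The concern holds. Table 2 omits the one organ system in the SAP's own irAE definition that has no other matching class, and the irAE tables follow from that list. Followed as written, the rule can under-count irAEs.

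The omission is certain; its consequence is bounded and may be nil. It needs an event that is coded to Nervous system disorders and was not marked on the CRF. At risk are the irAE label and count, not the record of the event. Safety analyses are descriptive (protocol 15.5), so no primary endpoint, alpha or power figure changes. The percentage-point figures above rest on the assumed Safety Set size and show scale only. The sponsor should correct this because the inconsistency is clear and the correction is cheap.

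**What to change.** In SAP 11.5:

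- add Nervous system disorders to Table 2 and change 17 to 18 in the text;
- delete the word *exhaustive*, unless the review is extended to all SOCs;
- keep the planned source indicator (CRF or sponsor-defined) in the irAE listing, so that any event found through the added class can be seen.

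This means one table row, one number and one word. The real cost is sponsor medical review of the already coded events in that SOC, in the context of dosing, concomitant medications and other AEs. The documents do not say how many there are. No new data field is needed.

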**Table 2 List of MedDRA SOCs Used by Sponsor in Identification of Additional Potential irAEs**

MedDRA SOCs
Cardiac disorders
Endocrine disorders
Eye disorders
Gastrointestinal disorders
General disorders and administration site conditions
Hepatobiliary disorders
Immune system disorders
Injury, poisoning and procedural complications
Investigations
Musculoskeletal and connective tissue disorders
Neoplasms benign, malignant and unspecified (incl cysts and polyps)
Product issues
Renal and urinary disorders
Respiratory, thoracic and mediastinal disorders
Skin and subcutaneous tissue disorders
Surgical and medical procedures
Vascular disorders

The number and percentage of subjects who experienced at least one irAE will be tabulated. The preferred terms will be identified using the search strategy as described above. The frequency and percentage of immune-related TEAEs will be summarized by PT, as well as by PT and maximum grade. Similar analyses will be repeated for Grade 3 or above immune-related TEAEs and for Grade 3 or above treatment-related immune-related TEAEs. The frequency and percentage of treatment-related immune-related TEAEs will be summarized by PT and maximum grade.

Similarly, the frequency and percentage of immune-related serious TEAEs will be summarized by PT and maximum grade. Similar analysis will be repeated for Grade 3 or above immune-related serious TEAEs by PT. The number and percentage subjects who experienced immune-related TEAEs leading to permanent discontinuation of IMO-2125 and

Idera Pharmaceuticals, Inc.  
 Statistical Analysis Plan  
 Protocol Number: 2125-MEL-301

---

subjects who experienced immune-related TEAEs leading to permanent discontinuation of ipilimumab will be presented by PT.

A listing of immune-modulating medications which include thyroid hormone replacement therapies, systemic steroid and immuno-suppressants used after occurrence of irAE will be presented. Thyroid hormone replacement therapies will be identified by WHO drug ATC prefix H03, systemic steroids by WHO drug ATC prefix H02, and immuno-suppressants by WHO drug ATC prefix L04.

All irAEs will be listed. This listing will include treatment arm, age, sex, verbatim term and the corresponding coded terms, start date and study day, end date and study day, grade, serious (yes or no), relationship to treatment (yes or no), action taken, and outcome. It will also include an indicator for the source of the irAEs (CRF or sponsor-defined).

The following summaries will be provided:

- Immune-Related Treatment-Emergent Adverse Events by Preferred Term
- Immune-Related Treatment-Emergent Adverse Events by Preferred Term and Maximum Grade
- Grade 3 or Above Treatment-Related Immune-Related Treatment-Emergent Adverse Events by Preferred Term
- Treatment-Related Immune-Related Treatment-Emergent Adverse Events by Preferred Term and Maximum Grade
- Grade 3 or Above Treatment-Related Immune-Related Treatment-Emergent Adverse Events by Preferred Term
- Immune-Related Serious Treatment-Emergent Adverse Events by Preferred Term and Maximum Grade
- Grade 3 or Above Immune-Related Serious Treatment-Emergent Adverse Events by Preferred Term
- Immune-Related TEAEs Leading to Permanent Discontinuation of IMO-2125 by Preferred Term
- Immune-Related TEAEs Leading to Permanent Discontinuation of Ipilimumab by Preferred Term

The following listing will be provided:

- Immune-Related Treatment-Emergent Adverse Events

## **11.6 ADVERSE EVENTS OF SPECIAL INTEREST**

Systemic injection and infusion reaction such as cytokine release syndrome (CRS), anaphylactic and anaphylactoid reactions are deemed to be adverse events of special interest

Idera Pharmaceuticals, Inc.  
 Statistical Analysis Plan  
 Protocol Number: 2125-MEL-301

(AESIs). From communication with U.S. Food and Drug Administration (FDA) on 11 September 2020, the agency agreed with the Sponsor regarding the use of the American Society for Transplantation and Cellular Therapy (ASTCT) Consensus (Lee, 2019) for assessment of CRS events, and FDA’s guidance for the industry for immunogenicity assessment for evaluation of anaphylactic events. FDA recommended to assess any fever (not attributable to any other cause), hypotension and hypoxia, and to include related organ toxicities associated with CRS with severity graded according to CTCAE 4.03. FDA also recommended to include definitions of CRS, anaphylaxis, and hypersensitivity based on clinical diagnostic criteria and to provide an analysis based on the clinical criteria to distinguish CRS from anaphylaxis and hypersensitivity by presenting data on the nature, onset, frequency and severity, information about dose modifications and any evidence of recurrence with dose reduction or after drug withdrawal.

The Sponsor has used the following nine MedDRA LLTs for the initial database search for AESIs reported within 14 days after any tilso injections: anaphylaxis, cytokine release syndrome, infusion related reaction, injection site allergic reaction, injection related reaction, allergic reaction, anaphylactic reaction, anaphylactoid reaction, or systemic inflammatory response syndrome. A listing of AEs corresponding to these LLTs was generated to be used for evaluation against the ASTCT definition for CRS as well as the FDA guidance document on anaphylactic reaction which are provided below as a reference:

AE Term	Definition
CRS	A supraphysiologic response following any immune therapy that results in the activation or engagement of endogenous or infused T cells and/or other immune effector cells. A qualified CRS event will include fever along with hypotension and/or hypoxia.
Fever	A disorder characterized by elevation of the body’s temperature above the upper limit of normal, and a temperature of 38.0 °C is considered grade 1 fever.
Hypotension	A disorder characterized by a blood pressure that is below the normal expected for an individual in a given environment.
Hypoxia	An Oxygen saturation (SaO 2 ) <94% or an individual requiring supplemental oxygen to correct a deficit in oxygenation is considered to have hypoxia. Oxygen provided only as a comfort measure should not be used.
Anaphylactic reaction	Anaphylaxis is a serious, acute allergic reaction without a particular immunologic mechanism and based on the following clinical features: 
 
1. Acute onset of an illness (minutes to several hours) with involvement of the skin, mucosal tissue, or both, and at least one of the following:               
 
• Hypoxia
 
• Hypotension
 
 
 
2. Two or more of the following that occur rapidly after exposure to Tilsotolimod (minutes to several hours):               
 
• Involvement of the skin-mucosal tissue
 
 
 

Idera Pharmaceuticals, Inc.  
 Statistical Analysis Plan  
 Protocol Number: 2125-MEL-301

AE Term	Definition
	
 
• Hypoxia
 
• Hypotension
 
• Persistent gastrointestinal symptoms
 

	
 
3. Hypotension after exposure to Tilsotolimod when prior systemic reactions with Tilsotolimod has occurred (minutes to several hours)
 

In order to perform a more comprehensive assessment of the AESIs, a search of all TEAEs which are coded under any of the following MedDRA SOC and started within 14 days after any tilsotolimod injections will also be conducted:

- General disorders and administration site condition
- Respiratory and mediastinal disorders vascular disorders
- Immune system disorders (see [Table 2](#) in Section 11.5)

The AEs identified will be reviewed and classified by the Sponsor as CRS, anaphylactic reaction or hypersensitivity reaction. The classification will be imported into the analysis dataset for summaries.

Significant AESIs will be summarized, that include Grade 3 and above systemic injection and infusion reactions.

Based on the strategy and definitions stated above, these AEs included under each event type will be determined based on a programmatic search of the AE datasets using the specified LLT in conjunction of a medical review of the AEs identified. The incidence of the AESIs under each event type will be summarized by MedDRA preferred term.

Analyses of time to the first onset of the AESIs will be analyzed using the Kaplan-Meier product-limit method to estimate the quartiles and corresponding 95% confidence intervals for time to onset of each event. For this analysis, subjects who completed or prematurely terminated the study with the specified event will have the time to onset censored at the time of their completion or termination.

A listing of subjects who were identified to have experienced AESIs will be presented with onset, frequency and severity, information about dose modifications and any evidence of recurrence with dose reduction or after drug withdrawal.

Subject ID	PT	Sponsor assessed category	Grade	SAE	Time to Onset	Frequency	Recurrence after dose modification	Recurrence after drug withdrawal	Related Organ Toxicities and grades	Outcome
------------	----	---------------------------	-------	-----	---------------	-----------	------------------------------------	----------------------------------	-------------------------------------	---------

Abbreviation: PT = Preferred Term.

The following summaries will be provided:

- Significant Treatment-Emergent Adverse Events of Interest by Preferred Term

Idera Pharmaceuticals, Inc.  
Statistical Analysis Plan  
Protocol Number: 2125-MEL-301

---

- Time to Onset of Significant Treatment-Emergent Adverse Events of Interest

The following listing will be provided:

- Significant Treatment-Emergent Adverse Events of Interest

